### 3 Materials And methods

#### 3.1 Design:

This study is prospective, open label, non-randomized, non-comparative and observational.

This study protocol includes 12 one-hour training RAGT sessions during 4 weeks three times per week, under the supervision of qualified rehab team.

Informed consent will be obtained from patients prior to inclusion in the study, which will be carried out in accordance with the Declaration of Helsinki.

#### 3.2 Inclusion and exclusion Criteria

Subjects will be evaluated for their eligibility from neurorehabilitation and neurology outpatient clinics at the Multiple Sclerosis Center of Catalonia (Cemcat).

##### 3.2.1 Inclusion criteria

- Male or female, between 18 and 65 years of age
- Confirmed diagnosis of MS
- EDSS from 6.0 to 7.0
- Able to verticalize on a daily basis
- Stable course of disease-modifying therapy over the past 6 months
- Clinical comorbidity asymptomatic (i.e., no underlying cardiovascular disease)
- Height: between approximately 1.60 and 1.90 m.
- Willingness to visit the Multiple Sclerosis Center of Catalonia (Cemcat) for testing and training.
- Gait disorder conditioned by paresis or hemiparesis associated with ataxia or sensory problems
- Patient having given written consent
- Atalante is able to accommodate the following limb lengths:
- Thigh: 380-460mm
- Distance between the ground and the joint space of the knee (to be measured while wearing the shoes they intend to wear with Atalante):
  - 457–607mm for patient with an ankle dorsiflexion  $\geq 16^\circ$
  - 457–577mm for patient with an ankle dorsiflexion between  $13^\circ$  et  $16^\circ$
  - 457–567mm for patient with an ankle dorsiflexion between  $10^\circ$  et  $13^\circ$
  - 457–557mm for patient with an ankle dorsiflexion between  $0^\circ$  and  $10^\circ$
- Hip with less or equal to 460mm when seated
- Maximum weight:90 kg

##### 3.2.2 Exclusion criteria

- Pregnancy
- Starting or switching from fampridine (Fampyra®) in the last 4 weeks
- Height and weight outside the secure standard of safe use, described in the safety guides
- Contraindications to training with Atalante (eg, bone instability, history of osteoporosis or osteoporotic fractures)
- Subjects under Corticosteroids treatment or relapse

- Changes in disease-modifying and symptomatic therapy for MS during the study period
- Subjects with psychiatric or cognitive comorbidities that may interfere with the trial
- Whose joint centers cannot be aligned Atalante's
- Ranges of motion below:
  - Knee: 5° extension, 110° flexion
  - Ankle: 0° dorsiflexion, 9° plantar flexion, 18° inversion and eversion
  - Hip: 115° flexion, 15° extension, 17° abduction, 10° adduction, 10° medial rotation, 20° lateral rotation
- Severe spasticity (greater than Ashworth 3) or uncontrolled clonus
- Severe concurrent medical diseases: infections, circulatory, heart or lung, pressure sores
- Active implantable medical device

### 3.3 Enrollment and Screening

Subjects will be evaluated for their eligibility from neurorehabilitation and neurology outpatient clinics at the Multiple Sclerosis Center of Catalonia (Cemcat).

Potential subjects will be referred to the study via Cemcat Physicians. A member of the research team will screen the referral and confirm they meet the necessary inclusion and exclusion criteria. Following confirmation of criteria, potential subjects will be contacted by phone to schedule an initial visit for consent and baseline assessment.

Prior to all testing, each of the 20 selected participants will have time to read the consent form and ask questions (see Draft Informed Consent). The consent process will take place at the Multiple Sclerosis Centre of Catalonia (Cemcat, Vall d'Hebron Barcelona Hospital Campus, [name]).

### 3.4 Assessments

The following information will be collected for all patients: age, gender, weight, height, type of MS, years from the diagnosis, Expanded Disability Status Scale (EDSS) and type of support device.

For the correct evolution of the training sessions will be assessed the Arterial pressure and the heart rate before each training session. As well as the level of global fatigability by Modified fatigue scale (MFIS) and the physical effort of each session by means of the scale of perception of the effort R.P.E of Borg at the end of each training. We will also monitor the appearance of pain in any part of the body related to the RAGT at end of each training session using a pain registry (type of pain, location, intensity).

To reduce the incidence of any type of muscle injury the physical therapist before each RAGT session will assess the level of spasticity using the modified Ashworth scale and the Penn spasm frequency scale.

We will report the process metrics: the rate of potential candidates referred, do not meet device-related criteria (height, weight, or leg length segments), The rate of patient rejection of the device or protocol, Ratio of assistance and missed sessions and expectative of patients at begin of this study.

We will use a FUREO framework for Assessment of the Usability of Lower-Extremity Robotic Exoskeletal Orthoses to facilitate futures comparatives whit other robots strategies , using some modules as health outcomes module, device module, external and internal factor module, adding patients and professional acceptability modules, furthermore assessing cognition disability and type of personality.

A record of any unexpected Serious Adverse Events (SAE) within trial episodes will be keep. These are defined as death, a life-threatening adverse event or an event occurring as a result of the use of the device that requires medical intervention.

[figure not shown]
Type outcome	Test	Baseline (T1)		RAG Session 1-12 (S1-S12)		end of training (T2)	
		CRO	PROMs	CRO	PROMs	CRO	PROMs
Pain	1 Pain registry		x		x		x
Physiologic indicators	2 Heart rate	x		x		x	
	3 Arterial pressure	x		x		x	
Bowel function	4 Neurogenic Bowel Dysfunction NBD score Spanish version (NBD)	x				x	
Effort	5 Rating perception exertion The Borg R.P.E scale				x		
Fatigue:	6 Modified fatigue scale (MFIS)		x				x
Depression	7 Hospital Anxiety and Depression Scale (HADS)		x				x
User satisfaction	8 Gagnon questionnaire score user Evaluation of Satisfaction with assistive technology (QUEST) score		x			x	
	9 Satisfaction Quebec user Evaluation of Satisfaction with assistive technology (QUEST)						x
Health-related quality of life	10 MSQoL 54 Health Survey	x					x
Mobility	11 Rivermead Mobility Index	x				x	
Disability	12 Expanded Disability Status Scale (EDSS) de Kurtzke	x				x	
Balance	13 Berg scale test	x				x	
Spasticity	14 Ashworth assess by physiotherapist at start of each training day	x				x	
	15 Pen spams scale	x		x		x	

IC, Informed consent; Patient-Reported Outcome Measures (PROMs), Clinic report, CRO;

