### 2.2 Secondary Aims:

To describe **safety** of Robotic-Assisted Gait therapy (RAGT) using the Atalante self-balance exoskeleton for persons with multiple sclerosis (PwMS).

We consider safety as the low occurrence or not appearance of adverse effects.

- Defining a low occurrence as the appearance of an adverse effect related to the rehabilitation program in less than 10% of the reported patients. Defining an adverse event later in the chapter on instructions for reporting adverse events
- The occurrence of pressure ulcers more than grade 1 in more than 10% of reported patients. Not taking into account the pressure zones that can be considered as an acceptable effect within the program as long as it is reversible in minutes after the program.

To describe the effect at the functional level of RAGT using the Atalante self-balance exoskeleton for improving **Balance outcome, Walking speed, quality of life, depression**.

- Balance: We will assess the effect of RAGT at the balance outcome measured by the Berg scale, considering a clinically relevant change for improvement in balance as measured by BBS was +3 points, meaning that PwMS are likely to perceive that as a reproducible and clinically important change in their balance performance.

- Walking speed: We will assess the effect of RAGT at the walking speed measured by the 10 meters walking test, considering a clinically relevant change as an improvement of 20% of the score with respect to the baseline assess.
- Physiological Changes: We will observe the effect of RAGT at the bowel function using the Neurogenic Bowel Dysfunction Spanish version, (NBD) and Patient Global Impression of Improvement (PGI-I). considering a clinically relevant change of +3 points at NBD.

To describe the effect at the self-perception and psychological level of RAGT using the Atalante self-balancing exoskeleton to improve quality of life and depression.

- Using the Multiple Sclerosis Quality of Life-54 (MSQoL 54 Health Survey Spanish version) and Hospital Anxiety and Depression Scale (HADS) considering a clinically relevant change of 1.7 points at HADS

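### The safety criteria count every program-related adverse effect and ulcers above grade 1, but the only adverse-event record described is for unexpected serious events, no skin grading is listed, and the ulcer bullet runs against the definition above it

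*Protocol*

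**What the plan says.** Section 2.2 sets the concept first: "We consider safety as the low occurrence or not appearance of adverse effects". Two bullets follow.

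- The first defines low occurrence as "the appearance of an adverse effect related to the rehabilitation program in less than 10% of the reported patients". It leaves the definition of an adverse event to a later chapter on reporting instructions.
- The second reads "The occurrence of pressure ulcers more than grade 1 in more than 10% of reported patients", and sets aside pressure zones that disappear within minutes of the program.

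Section 3.4 describes what is collected. On adverse events it says: "A record of any unexpected Serious Adverse Events (SAE) within trial episodes will be keep". It goes on: "These are defined as death, a life-threatening adverse event". A third category completes the definition, namely "an event occurring as a result of the use of the device that requires medical intervention". Pain is handled separately: "We will also monitor the appearance of pain in any part of the body related to the RAGT", at the end of each session. The section also adopts parts of a usability framework, "using some modules as health outcomes module" among others, without saying what that module records.

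Rows 1 to 15 of the assessment table cover baseline, sessions 1 to 12 and end of training. None is an adverse-event row or a skin row. Section 3.4.1 adds a follow-up four weeks after the program, which has no column in the table.

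**The concern.** A safety proportion is only as good as the record behind its numerator. Here the criterion is wide (any related effect, serious or not, expected or not) and the described record is narrow (unexpected and serious). The ulcer criterion needs a grade and a way to tell a lasting lesion from a transient pressure zone, and no skin assessment is listed. The chapter that would have closed these gaps does not exist in the document: the index goes from Intervention to Statistical considerations to References, and so does the text.

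The direction of the ulcer bullet is a separate fault. Under a definition of safety as low occurrence, it names a rate above 10%.

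At stake is whether the study can report its own safety criterion reliably. If related effects go unrecorded and the denominator is fixed, the observed rate can only fall, which favours the device. An analysis plan cannot repair this later, because it cannot recover events that were never written down.

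**Working it through.** **Inputs.** Limit of 10%, first bullet *less than*, second bullet *more than* (section 2.2). Sample sizes 15 (section 4) and 20 (section 3.3). Wilson intervals for proportions (section 4). The protocol gives no expected adverse-effect rate and no safety calculation to reproduce; its figure of 15 concerns walking performance and is used here only as a sample size.

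**Step 1: criterion against record.**

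| Event | In a section 2.2 criterion? | Record stated in section 3.4? |
|---|---|---|
| Device-caused, needs medical intervention, unexpected | yes | yes |
| Same, but expected | yes | none stated |
| Related, not serious, not pain | yes | none stated |
| Training-related pain | not stated | yes, pain registry each session |
| Ulcer above grade 1, unexpected, needs medical intervention | yes | yes, but no grade specified |
| Any other ulcer above grade 1 | yes | none stated |

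Blood pressure, heart rate, spasticity and exertion are also measured, but none of these is a record of adverse effects in general or of skin.

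**Step 2: how many affected patients the first criterion allows.** It is met when x/n < 0.10.

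- n = 15: 1/15 = 6.7%, met; 2/15 = 13.3%, not met.
- n = 20: 1/20 = 5.0%, met; 2/20 = 10.0%, not met.

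The largest permitted count is 1 at both sizes. If the true count is 2 and one of those patients is unrecorded, the label changes from not met to met. With a true count of 0 or 1 nothing changes. With 3, two patients would have to be missed.

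**Step 3: precision.** Wilson 95% limits are [p + z²/2n ± z√(p(1−p)/n + z²/4n²)] / (1 + z²/n), with z = 1.96. For 1/15:

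- centre (0.0667 + 0.1281)/1.2561 = 0.155
- half-width 1.96 × √(0.00415 + 0.00427)/1.2561 = 0.143
- limits 1.2% to 29.8%

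| Affected | n = 15 | n = 20 |
|---|---|---|
| 0 | 0% (0 to 20.4%) | 0% (0 to 16.1%) |
| 1 | 6.7% (1.2 to 29.8%) | 5.0% (0.9 to 23.6%) |
| 2 | 13.3% (3.7 to 37.9%) | 10.0% (2.8 to 30.1%) |

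Even with no events the upper limit lies above 10%, so the label describes the sample and does not show that the rate is under 10%.

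**Step 4: ulcer bullet.** As worded it is true from 2/15 (13.3%) or 3/20 (15.0%) upwards and false at zero. The sentence above it describes the opposite.

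**Step 5: denominator.** The bullets use *reported patients* without defining them, and section 3.4.1 drops anyone who misses three consecutive sessions. If 2 of 20 are affected and one of them is dropped and left out, the figure becomes 1/19 = 5.3%, and the criterion is met instead of not met.

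**The case against.** The strongest reply is that non-recording is inferred. Section 3.4 says that a record of serious events will be kept; it does not say that other effects will not be. Section 2.2 commits to a proportion and refers to reporting instructions, so the intent to collect is clear. That stands: a reader might infer that non-serious effects will be lost, and the protocol supports only that no record of them is stated. In the same way, the assessment table is not a full list of what is collected (the 10-metre walk named in section 2.2 is not among its rows). The absence of a skin row therefore shows that skin grading is not listed, and no more. The third limb of the serious-event definition could also catch some treated ulcers.

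A reader might also take the ulcer bullet literally, so that frequent ulcers count as safe. The sentence above it rules that out, and the bullet may be meant as a failure threshold. But the text does not say so, and the wording still needs to be reconciled.

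A third tempting reading is that the two bullets leave a gap at exactly 10%. They do not. They concern different events, and each settles that value on its own: 2/20 is not below 10% for the first and not above 10% for the second.

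Finally, safety is a secondary, descriptive aim with no test. That limits the weight of the point but does not remove it, because the mismatch lies in what is recorded and not in how it is analysed.

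**Conclusion.** The point holds, and the protocol should be changed. The described adverse-event record cannot by itself supply the numerator of the first safety criterion, the ulcer criterion has no listed measurement, the promised definition is absent, and the ulcer bullet conflicts with the concept it serves. The under-10% criterion may therefore be reported as met on an incomplete count.

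On size: one affected patient is allowed at 15 or at 20, and one unrecorded patient reverses the label only when the true count is exactly two. That under-recording can only favour the device assumes a fixed denominator, which the protocol does not secure. The number of events that would go unrecorded is not in the document and is not estimated here. The conclusion rests on the text as written; working instructions kept elsewhere could narrow the gap in practice, but the protocol cites only a chapter that it does not contain.

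**What to change.** **Section 3.4, recording.** Replace the serious-only record with a record of all adverse events, serious or not and expected or not, each with its seriousness and its relatedness to the program. Keep the protocol's existing definition of a serious event as a subset.

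**Definition.** Supply the adverse-event definition that section 2.2 promises. Use one term throughout, either *adverse effect* or *adverse event*, and point section 2.2 to the place where it is defined. State whether registered pain counts towards the 10%.

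**Schedule.** Add an adverse-event row and a graded skin-status row at the sessions and at end of training. Name the grading scale, and time the check so that reversible pressure zones can be told apart from lesions. If events are also recorded at the four-week follow-up, add that column.

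**Section 2.2, ulcer bullet.** Reconcile its direction with the low-occurrence definition, either as a criterion for safety or explicitly as a failure threshold.

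**Denominator and reporting.** Define *reported patients*, including how those dropped under section 3.4.1 are counted. Report both proportions with the Wilson intervals already planned.

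**Cost.** Slightly more case-report work, mainly at sessions that staff already supervise, plus some at follow-up if that visit is included. The observed safety rate may turn out less favourable.

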### 3.4.1 Schedule

Following completion of day 1 assessments, all subjects will be scheduled for the intervention phase of the study, each participant will receive 12 sessions of RAGT scheduled ideally for three times a week for 4 weeks. If a subject cancels a treatment session, it will be counted as missed session. If a subject misses three consecutive treatment sessions, they will be dropped from the study due to inconsistency in treatment carryover. Cancellations and changes in patient scheduling represents a true clinical environment and represents normal clinical patient management.

At the end of RAGT, a new exploration will be carried out to evaluate the initial parameters. A follow-up will be carried out 4 weeks after the rehabilitation protocol has ended.

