## 2 Aims

### 2.1 Primary Aim:

To describe **usability** of Robotic-Assisted Gait therapy (RAGT) using the Atalante self-balance exoskeleton for persons with multiple sclerosis (PwMS) and explore patient characteristics related to this feature.

Defining usability as a quality attribute that evaluates the ease of use of user interfaces, evaluating the perspective of patients by the Satisfaction Quebec user Evaluation of Satisfaction with assistive technology (QUEST) score and a questionnaire specific to the use of Atalante device.

We have defined high Usability as: Obtaining a positive score greater than or equal to 70% of the total possible score on the Satisfaction Quebec user Evaluation of Satisfaction with assistive technology (QUEST) score.

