## 4 Statistical considerations

The sample size calculation was based on the observed success rate (70%) in a previous evaluation of safety and performance of the self-balancing walking system Atalante in patients with spinal cord injury (i.e., 10 mWT with continuous walking mode)

A sample size of 15 patients had been deemed necessary to demonstrate the performance with an alpha risk of 5% and a statistical power of 80% (Two-sided test).

Descriptive statistics (i.e., mean, standard deviation) will be calculated for quantitative data (demographics and clinical characteristics and outcome measures). Frequencies will be calculated for qualitative variables. For the proportions, binomial proportion confidences will be calculated using the Wilson formulae. Proportions will be compared using the Newcombe formulae

The Wilcoxon bilateral matched-pairs test will be used to compare repeated measurement on a single sample (mean, standard deviation).

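### Participants who miss three consecutive sessions leave the study before the only scheduled post-training QUEST, so the high-usability proportion is at risk of upward bias

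*Protocol*

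**What the plan says.** - **Primary outcome.** Section 2.1 defines high usability as a QUEST score "greater than or equal to 70% of the total possible score".
- **Timing of QUEST.** In the assessment table of section 3.4, row 9 ("9 Satisfaction Quebec user Evaluation of Satisfaction with assistive technology (QUEST") has a single mark, at end of training (T2). Row 8 ("8 Gagnon questionnaire score user Evaluation of Satisfaction with assistive technology (QUEST) score") is marked at baseline (T1) and at T2. Neither row is marked for sessions 1 to 12.
- **Removal rule.** Section 3.4.1 states "If a subject cancels a treatment session, it will be counted as missed session" and then "If a subject misses three consecutive treatment sessions, they will be dropped from the study due to inconsistency in treatment carryover". It makes no distinction by reason. The re-assessment it describes takes place once training has ended, and nothing is described for participants who stop early.
- **Process metrics.** Section 3.4 promises to report "The rate of patient rejection of the device or protocol, Ratio of assistance and missed sessions", among other items, but does not tie these to the QUEST proportion.
- **Numbers.** Section 3.3 says "each of the 20 selected participants will have time to read the consent form" and section 4 says "A sample size of 15 patients had been deemed necessary". The protocol does not present the difference as a dropout allowance.

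**The concern.** The outcome is satisfaction with a device, and repeated absence can itself be a sign of dissatisfaction. The protocol monitors fatigue, effort and pain, all plausible reasons for not coming back. The rule removes these participants from the study, not only from training, and it acts before the one point at which QUEST is due. The baseline mark on row 8 does not help, because it falls before any training session.

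Two things are at stake. If dropped participants rate the device lower than completers, the reported high-usability proportion is too high. The primary aim also includes exploring patient characteristics related to usability, and the people lost may be among the most informative for that question.

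**Working it through.** **Is any post-use score planned for a dropped participant?** Set the sections side by side:

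1. Section 2.1: the outcome is QUEST.
2. Section 3.4, table: QUEST is marked at T2 only. Row 8 adds T1, which precedes the intervention phase.
3. Section 3.4.1: a participant with three consecutive missed sessions is no longer in the study at T2.

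Together these leave no scheduled QUEST after device use for such a participant.

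**How large could the bias be?** The protocol states neither a dropout rate nor an expected proportion with high QUEST, so it has no figure of its own to reproduce. The inputs below are assumptions:

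- *d*, the fraction dropped: 10% to 25%. The upper end equals (20 − 15)/20, used only as a convenient outer value.
- *p_c*, the proportion of completers scoring high: 70%. This is illustrative. In the protocol, 70% is a per-participant score threshold (section 2.1) and a 10-metre walk success rate in spinal cord injury (section 4), not an expected QUEST proportion.
- *p_d*, the proportion of the dropped who would score high: 0 to 70%.

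The value over all starters is (1 − d)·p_c + d·p_d, so

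overstatement = p_c − [(1 − d)·p_c + d·p_d] = d·(p_c − p_d).

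| d | p_d = 0 | p_d = 0.25 | p_d = 0.50 | p_d = 0.70 |
|---|---|---|---|---|
| 10% | 7.0 | 4.5 | 2.0 | 0 |
| 15% | 10.5 | 6.75 | 3.0 | 0 |
| 20% | 14.0 | 9.0 | 4.0 | 0 |
| 25% | 17.5 | 11.25 | 5.0 | 0 |

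(percentage points; for example 0.25 × (0.70 − 0.50) = 5.0)

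**In counts, for 20 starters**, with the Wilson 95% intervals that section 4 specifies:

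- *2 dropped, 13 of 18 completers high.* Reported: 13/18 = 72% (49 to 88%). Over all starters, the value lies between 13/20 = 65% (none of the dropped high) and 15/20 = 75% (both high).
- *5 dropped, 11 of 15 completers high.* Reported: 11/15 = 73% (48 to 89%). Over all starters, the value lies between 11/20 = 55% and 16/20 = 80%. Reported minus all-starters is +18.3, +13.3, +8.3, +3.3, −1.7 and −6.7 points if 0, 1, 2, 3, 4 or 5 of the dropped would have scored high.

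**The extreme case from the other direction.** Suppose 14 of 20 starters (70%) would truly score high and every dropped participant is among the other six. Completers then show 14/18 = 77.8% with 2 dropped and 14/15 = 93.3% with 5 dropped.

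**The case against.** **The table is an imperfect guide.** Row 14 (Ashworth) carries a label saying it is assessed each training day but has no mark for sessions 1 to 12. The text groups the fatigue scale with the per-session measures, while the table marks it only at T1 and T2. An absent mark is therefore weak evidence, and nowhere does the protocol say that a dropped participant gets no exit questionnaire. This is fair, but no text places QUEST during the sessions or at discontinuation either, and removal is from the study.

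**Other data might exist.** Section 3.4 mentions acceptability modules under the FUREO framework, and section 3.4.1 a follow-up 4 weeks after training. The modules have no timing and the follow-up has no stated content. Neither puts a QUEST in front of someone already dropped.

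**The rule may rarely bite.** At three sessions a week it takes a full missed week. That limits how many participants are affected, not what happens to their data.

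**The bias is conditional and its size assumed.** This stands. Nothing in the protocol shows that absence and satisfaction are linked, and the direction can reverse. At 10% dropped, 2 to 7 points is small beside an interval of 49 to 88%. But a wide interval does not allow for systematic loss, and without a score or a recorded reason the sponsor could not show which case applies.

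**Denominators and sensitivity analyses belong to an analysis plan.** Largely true, and one may exist. Their absence from the protocol is not the complaint. The removal rule and the assessment schedule are protocol matters, and they decide whether the score exists at all.

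**Conclusion.** The concern holds. As written, the plan schedules no post-use QUEST for anyone removed after three consecutive missed sessions, and no later analysis can recover it. That follows from the text and is firm. Upward bias is a risk, not a certainty: it requires that dropped participants be less satisfied than completers. With 70% of completers high and none to half of the dropped high, the overstatement is 2.0 to 7.0 points at 10% dropped and 5.0 to 17.5 points at 25%. It is zero if the two groups score alike and negative if the dropped score better. All of these rates are assumptions. The promised rejection rate and missed-session ratio would reveal the loss but would not correct the proportion. The change should be made, since it protects the primary outcome at little cost.

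**What to change.** Leave the training rule as it stands and change only its consequence for data collection.

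1. In section 3.4.1, say that these participants stop training but remain in the study for assessment.
2. In the section 3.4 table, add a discontinuation column or footnote: QUEST and, where possible, the other T2 assessments, with the reason for stopping recorded.
3. In section 4 or the analysis plan, report the high-usability proportion over all participants who started at least one session, next to the completers-only figure. Add a sensitivity analysis that counts any QUEST still missing as not high.

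A related point needs only reconciling: section 3.2.2 lists therapy changes during the study as an exclusion. The sponsor should state how this applies after enrolment and whether such participants still complete QUEST.

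The cost is one sentence, one column or footnote, one line on analysis, and one extra questionnaire per discontinued participant: 2 to 5 in total if 10 to 25% of 20 stop. Some may decline it, and the reported usability figure may come out lower.

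### Dropping subjects from the study after three consecutive missed sessions leaves them without a QUEST score, so the primary-outcome sample is selected on attendance

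*Protocol*

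**What the plan says.** Section 3.4.1 plans that "each participant will receive 12 sessions of RAGT scheduled ideally for three times a week for 4 weeks". On missed visits it says "If a subject cancels a treatment session, it will be counted as missed session", with no exception for the reason, and then "If a subject misses three consecutive treatment sessions, they will be dropped from the study due to inconsistency in treatment carryover". The sanction is removal from the study, not only from training. The same paragraph accepts cancellations and rescheduling as ordinary clinical management.

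Section 2.1 defines high usability by QUEST alone: "Obtaining a positive score greater than or equal to 70% of the total possible score". The primary aim also covers the exploration of patient characteristics related to usability.

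In the assessment table of section 3.4, the row "9 Satisfaction Quebec user Evaluation of Satisfaction with assistive technology (QUEST)" has a single mark, at T2. The row above it, the Gagnon questionnaire, also carries QUEST in its label and is marked at T1 and T2. A T1 mark precedes training, so it cannot stand in for a rating after use. Berg, NBD, HADS, MSQoL-54 and Rivermead have their only post-training value at T2.

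Section 3.4 also lists process metrics, among them "The rate of patient rejection of the device or protocol, Ratio of assistance and missed sessions". Section 3.3 sets the number of participants: "each of the 20 selected participants will have time to read the consent form".

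**The concern.** In a usability study, failure to attend is plausibly part of the outcome. Pain, fatigue, spasticity and pressure effects are all things this protocol monitors, and any of them could make a patient with EDSS 6.0 to 7.0 cancel. If these patients leave before T2, the share with high usability and the T1–T2 changes describe those who tolerated the programme. The exploration of which patients find the device usable also loses its least favourable cases. With no control arm, no comparator would reveal the distortion.

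The stated reason, continuity of treatment effect, can justify stopping training. It does not justify withholding a satisfaction questionnaire from someone who has used the device. The rule also follows the pattern of misses and not the exposure: one missed week removes a subject who could otherwise attend 9 of 12 sessions, while scattered misses remove nobody, because total misses have no limit.

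**Working it through.** **Inputs from the protocol.** 12 sessions, three per week for 4 weeks; removal after three consecutive misses (one training week, 3/12 = 25% of sessions); 20 participants; QUEST at T2 only; Wilson intervals (section 4). The protocol gives no attendance or dropout rate, so there is no figure of its own to reproduce. Attendance of 90%, 80% and 70% is assumed below.

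**1. What the rule selects on.** Each subject has one of 2^12 = 4,096 attend/miss patterns.
- 1,705 patterns contain no run of three misses. The lowest attendance among them is 4 sessions (15 patterns).
- Ten patterns have exactly three misses, all in a row. Those subjects would have attended 9 of 12 sessions but are removed.
- Low exposure among retained subjects is uncommon. With independent misses, 0.3%, 4.0% and 13.6% of subjects stay with fewer than 8 sessions at 90%, 80% and 70% attendance, and fewer still if sessions are made up.

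**2. How many subjects meet the rule.** With miss probability m, sum m^k × (1 − m)^(12 − k) over all patterns that contain a run of at least three misses, where k is the number of misses. For clustered misses, use a first-order Markov chain with the same overall miss rate, P(miss after miss) = 0.4 (assumed) and P(miss after attendance) = 0.6m/(1 − m).

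| Attendance | Independent | Of 20 | Clustered | Of 20 |
|---|---|---|---|---|
| 90% | 0.0091 | 0.18 | 0.1004 | 2.01 |
| 80% | 0.0647 | 1.29 | 0.1964 | 3.93 |
| 70% | 0.1887 | 3.77 | 0.2875 | 5.75 |

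**3. Effect on the primary proportion.** Suppose 14 of 20 would report high usability: 14/20 = 70.0% (Wilson 95% interval 48.1 to 85.5).
- One lost: 13/19 = 68.4% if that subject would have rated high; 14/19 = 73.7% (51.2 to 88.2) if low.
- Four lost: 10/16 = 62.5% if all would have rated high; 14/16 = 87.5% (64.0 to 96.5) if all low.

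A case that crosses 70%: if 12 of 20 (60.0%, 38.7 to 78.1) would rate high and three low raters are dropped, the observed figure is 12/17 = 70.6%. With five dropped it is 12/15 = 80.0% (54.8 to 93.0). If loss is unrelated to usability, no bias is expected.

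**4. Does the larger enrolment help?** Section 4 calculates 15 subjects and section 3.3 selects 20. Since 15/(1 − 0.25) = 20, the margin would cover 25% loss in number. It does nothing about who is lost.

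**The case against.** The best case for the plan has five parts.

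- **Analysis can handle it.** High usability is a yes/no outcome, so dropped subjects can be counted as not reaching it, or best and worst cases shown over all who started. Such handling is commonly left to the SAP. This stands for the binary result. It does not supply their actual QUEST scores, their T1–T2 changes or their part in the exploration of patient characteristics.
- **The figures attribute too much to the rule.** Subjects who give up because they dislike the device may refuse T2 anyway, and those removed only by the rule may have been ill or lacked transport. Rescheduled sessions may not count as missed. All of this stands, and it makes the rule's own effect probably smaller than the upper figures.
- **The range is assumed.** At 90% attendance with independent misses the effect is practically nil, and the 0.4 in the clustered case has no source in the protocol. The shift from one lost subject (70.0% to at most 73.7%) is small against an interval of 48.1 to 85.5. This also stands. The size is unknown, and the direction is probable but not certain.
- **Tolerance is recorded elsewhere.** Pain, effort, blood pressure and heart rate are recorded at each session, serious adverse events are recorded, and device rejection and attendance are reported. These make the loss visible, but they do not correct the QUEST proportion.
- **A descriptive study may describe those who completed the programme.** That is a legitimate but narrower aim. Section 2.1 speaks of persons with multiple sclerosis, not of good attenders.

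**Conclusion.** The concern holds. As written, section 3.4.1 ends study participation after three consecutive misses, and the protocol provides no assessment at that point, so these subjects have no primary outcome. Under the assumed attendance rates this affects about 0 to 6 of 20 subjects. Losing four could turn a true 70.0% into anything from 62.5% to 87.5%; the upper end needs every removed subject to be a low rater. A favourable bias rests on the inference that poor attendance goes with poor usability or tolerance, which is plausible but not shown in the protocol. The change should be made, though the study does not fail without it: the harm is uncertain in size, but it touches the primary outcome and the lost assessments cannot be recovered afterwards. Confidence is medium.

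**What to change.** Reword the sentence in section 3.4.1 so that three consecutive misses may stop training but not study participation. Perform T2, including QUEST and adverse effects, in every subject who starts training, either at the planned end of the 4 weeks or when training stops. Include all of them in the results, and describe those results as following the sessions actually received, using the attendance already recorded.

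The continuity rule for training can stay. The cost is one sentence and T2 visits for a few poor attenders, about 0 to 6 of 20 under the assumptions used here. Results may look slightly less favourable. Some poor attenders may still decline T2, so the change reduces the selection but may not remove it.
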